17. QUALITY OF LIFE ANALYSIS

Quality of life analysis is as described in other secondary efficacy outcomes in [section 16.3.14](#).

Noven Pharmaceuticals, Inc.

Protocol HP-5000-US-07

Statistical Analysis Plan

Page 40 of 58

18. SAFETY OUTCOMES

Safety analyses will be conducted using data from the SAF population. Safety variables include AEs, clinical laboratory test results, body weight, vital signs, ECG readings, physical examination results, and dermal safety results. No formal inferential analyses will be conducted for safety variables, unless otherwise noted.

18.1 ADVERSE EVENTS

AEs will be coded using MedDRA version in effect at the time of final database lock.

TEAEs are defined as:

AEs that begin or pre-existing conditions that worsen at the time of or following the start of treatment with study drug through the Follow-up Visit or Early Termination Visit, whichever occurs first.

See [Appendix 2](#) for handling of partial or completely missing dates for AEs. In the case where it is not possible to define an AE as treatment emergent or not, the AE will be classified as the worst case, i.e., treatment emergent. Adverse event listings will display start and end dates as collected (even if partial) and they will be sorted by treatment group, subject ID, then by SOC/PT in alphabetical order.

The AE summaries that will be provided are described below in sub-sections [18.1.1](#) and [18.1.2](#). Additional details are included in the relevant table and listing shells.

Listings will include all adverse events.

18.1.1 ALL TEAEs

The incidence of TEAEs will be presented by SOC and PT and also broken down further by severity and relationship to study medication.

The number and percentage of subjects with at least one TEAE and the number of TEAEs the subjects had will be presented for each SOC and each PT within SOC by treatment group and all treated subjects. An additional summary of TEAEs will be provided for PTs occurring in at least 1% of subjects in HP-5000 arm and having a higher percentage of subjects in the HP-5000 Arm than the Placebo Arm, this summary will be presented by SOC and PT within SOC. Summaries will be presented by treatment group and in decreasing frequency. AEs which occur during the follow-up period after the last patch removal will be summarized separately by SOC and PT

Noven Pharmaceuticals, Inc.

Protocol HP-5000-US-07

Statistical Analysis Plan

Page 41 of 58

within SOC and treatment group.

18.1.1.1 Severity

The summary of TEAEs by SOC and PT will be expanded to show the number and percent of subjects and number of events by severity level. Severity is classified as “mild”, “moderate”, “severe”, or “life-threatening”. TEAEs with missing severity will be classified as “not specified”. If a subject reports a TEAE more than once within the same PT and SOC, the event with the worst-case severity will be used in the corresponding severity summaries.

18.1.1.2 Relationship to Study Medication

Relationship, as indicated by the Investigator, is classed as “not related”, “unlikely related”, “possibly related”, or “definitely related”. A “related” TEAE is defined as a TEAE with a relationship to study medication as “possibly related”, or “definitely related” to study medication. TEAEs with missing relationship to study medication will be classified as “related”. If a subject reports the same AE more than once within the same PT and SOC, the AE with the worst-case relationship to study medication will be used in the corresponding relationship summaries. A summary of related vs. non-related TEAEs by SOC and PT will be presented.

The number and percentage of subjects with at least one “related” AE (Adverse reaction by investigator) and the number of TEAEs the subjects had will be presented for each SOC and each PT within SOC by treatment group and all treated subjects. An additional summary of related AEs will be provided for PTs occurring in at least 1% of subjects in any treatment group. Summaries will be presented by treatment group and in decreasing frequency.

18.1.2 TEAEs LEADING TO DISCONTINUATION OF STUDY MEDICATION AND DISCONTINUATION FROM STUDY

AEs leading to early withdrawal or discontinuation of study medication will be identified by using the Adverse Events page of the eCRF, where item ‘Action taken with study treatment’ indicates permanent discontinuation of study medication, i.e., “Drug withdrawn”. AEs leading to early study withdrawal will be identified by using the Adverse Events page of the eCRF, where the answer to item ‘Did the AE cause the subject to discontinue from the study?’ indicates “Yes”.

For TEAEs leading to early study withdrawal or discontinuation of study medication, summaries of incidence rates (frequencies and percentages) by SOC and PT will be prepared. The listings of those AEs will be provided.

Noven Pharmaceuticals, Inc.

Protocol HP-5000-US-07

Statistical Analysis Plan

Page 42 of 58

18.1.3 SERIOUS ADVERSE EVENTS AND DEATH

Serious adverse events (SAEs) are those events recorded as “Serious” on the Adverse Events page of the eCRF. A summary of SAEs by SOC and PT will be prepared.

18.1.4 ADVERSE EVENTS LEADING TO DEATH

AEs leading to death are those events which are recorded as “Fatal” on the Adverse Events page of the eCRF. Deaths may also be recorded on the End of Study page of eCRF. A listing of all deaths will be prepared based on these sources.

18.1.5 TEAEs AT APPLICATION SITE

A summary table with TEAEs at application site will be presented by SOC and PT. This data will be collected from adverse event eCRF form. If the question “is the event at the application site?” is marked “yes”.

18.2 DEATHS

A listing of all deaths will be presented based on the section [18.1.4](#).

18.3 LABORATORY EVALUATIONS

The list of laboratory assessments to be included in the outputs is as in protocol [section 10.3.2.1.1](#). Results from the central laboratory for hematology, clinical chemistry, and urinalysis will be included in the reporting of this study. If central laboratory tests could not be performed, local laboratory results may be collected. All laboratory test results will be presented in SI units and listed using the sort order subject number, clinic visit number and relative study day (See the protocol [section 10.2](#) and SAP [section 6.1](#) for definitions.)

Quantitative laboratory measurements reported as “< X”, i.e. below the limit of quantitation (BLQ), or “> X”, i.e. above the upper limit of quantitation (ULQ), will be converted to X for the purpose of quantitative summaries, but will be presented as recorded, i.e. as “< X” or “> X” in the listings.

The following summaries will be provided for laboratory data for each parameter by treatment group and study visit:

Actual values and change from baseline (for quantitative measurements);

Noven Pharmaceuticals, Inc.

Protocol HP-5000-US-07

Statistical Analysis Plan

Page 43 of 58

Shifts from baseline according to normal/reference range criteria (for quantitative and categorical measurements).

18.4 ECG EVALUATIONS

The following ECG parameters will be reported for this study:

PR Interval (msec);

QRS Interval (msec);

QT Interval (msec);

RR Interval (msec);

QTcF Interval (msec) [derived by central ECG];

HR (bpm);

Overall assessment of ECG.

Should ECGs be collected in triplicate or multiple assessments on the same day, they will be analyzed as an average of the non-missing measurements on the same day. For the overall assessment, there are three possible results from the central cardiologist: 'Abnormal, Not Clinically Significant', 'Normal', and 'Abnormal, Clinically Significant'. All assessments will be summarized according to the worst non-missing assessment and categorized in the following order, "Normal", "Abnormal, Not Clinically Significant", "Abnormal, Clinically Significant".

The following summaries will be provided for ECG data for each parameter by treatment group and study visit:

Actual and change from baseline at Visit 8 (for quantitative measurements);

Shifts from baseline to worst overall ECG result.

18.5 VITAL SIGNS

The following vital sign measurements will be reported for this study:

Systolic blood pressure (mmHg);

Noven Pharmaceuticals, Inc.

Protocol HP-5000-US-07

Statistical Analysis Plan

Page 44 of 58

Diastolic blood pressure (mmHg);

Pulse rate (bpm);

Respiratory rate (breaths/min);

Body temperature;

Weight (kg);

BMI (kg/m²) [derived].

The following summaries will be provided for vital signs data for each parameter by treatment group and study visit:

Actual and change from baseline

BMI Weight Status Categories⁷

BMI (kg/m ²)	Weight Status
< 18.5	Underweight
18.5 ≤ BMI < 25.0	Normal
25.0 ≤ BMI < 30	Overweight
30.0 ≤ BMI	Obese

18.7 OTHER SAFETY ASSESSMENTS

18.7.1 DERMAL EVALUATIONS AT CLINIC

18.7.1.1 Patch Adhesion

Results of patch adhesion assessed at clinic and collected in the *Dermal Evaluations* eCRF form will be tabulated by visit and overall, for each treatment group. The frequency and percentage of patches in each category will be summarized, per the 5-point numerical scale described below, for each visit and overall. Also, for each patch adhesion score category, the number and percent of subjects with worst score in the specific category is presented by treatment group.

The following 5-point numerical scale is used to assess the patch adhesion:

Noven Pharmaceuticals, Inc.

Protocol HP-5000-US-07

Statistical Analysis Plan

Page 45 of 58

0 = ≥90% adhered (essentially no lift off the skin).
1 = ≥75% to <90% adhered (some edges only lifting off of the skin).
2 = ≥50% to <75% adhered (less than half of the system lifting off of the skin).
3 = <50% adhered but not detached (more than half the system lifting off of the skin without falling off).
4 = patch detached (patch completely off the skin).

18.7.1.2 Discomfort

Discomfort reported by the subjects will be collected in clinic on the *Dermal Evaluations* eCRF form. Number and percentage of subjects who report mild, moderate, severe, and no discomfort will be presented for each treatment group by visit and overall. The overall summary will show the number and percent of subjects with worst patch discomfort score in the specific category by treatment group. The scale used for assessment is as below:

0 = No discomfort
1 = Mild discomfort
2 = Moderate but tolerable discomfort
3 = Severe, intolerable discomfort
4 = Patch not present

Types of discomforts (itching, burning, pain, stinging, soreness, dryness, other) will be summarized and listed.

18.7.1.3 Irritation

Results of irritation assessment in clinic after patch removal as collected in *Dermal Evaluations* eCRF form using 2-part scales (Dermal Response and Other Effects) will be tabulated for each visit as a concatenated and combined score.

The following Berger and Bowman numerical scale is used to assess the Dermal Response:

- 0 = no evidence of irritation
- 1 = minimal erythema, barely perceptible
- 2 = definite erythema, readily visible; minimal edema or minimal papular response
- 3 = erythema and papules
- 4 = definite edema

Noven Pharmaceuticals, Inc.

Protocol HP-5000-US-07

Statistical Analysis Plan

Page 46 of 58

- 5 = erythema, edema, and papules
- 6 = vesicular eruption
- 7 = strong reaction spreading beyond the application site

The Other Effects will be scored via a letter as below:

- A (0) = slightly glazed appearance
- B (1) = marked glazed appearance
- C (2) = glazing with peeling and cracking
- F (3) = glazing with fissures
- G (3) = film of dried serous exudates covering all or part of the patch site
- H (3) = small petechial erosions and/or scabs
- N (0) = no other observations

[figure not shown]
The combined irritation score will be calculated as a numerical total; i.e., numerical “Dermal Response” score + numeric equivalent for the “Other Effects” lettered score (note that the “Other Notations” do not have numeric equivalents and do not contribute to the numeric Combined irritation score); e.g., 2N, 2A, and 3G will be reported as 2, 2, and 6 combined irritations scores respectively.

The frequency and percentage of subjects with patches in each combined and concatenated category will be summarized from the above scales at each visit and overall.

18.7.2 DERMAL EVALUATIONS AT HOME IN E-DIARY

At home, subjects will complete a questionnaire about adhesion, irritation, discomfort, and adhesive residue (on forms scheduled patch diary, unscheduled patch diary) in the eDiary. Data will be captured in the Scheduled Patch Diary Form and Unscheduled Patch Diary eCRF form. A by-subject listing of this data will be presented in addition to summary tables for the number of events for each of the dermal assessments such as adhesion, irritation, discomfort, and adhesive residue.

Additionally, the data regarding the adhesive residue at Visit 8 will be summarized based on the eCRF form Patch Removal at the site at the final visit.

Noven Pharmaceuticals, Inc.

Protocol HP-5000-US-07

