**At the clinical sites visits, investigators (or site personnel as appropriate) will conduct the following:**

**Visit 4 and Visit 5 (Week 1 and Week 2)**

1. Obtain vital signs measurements.
2. Administer the WOMAC questionnaire for the target knee.
3. Perform PGA.
4. Perform Patient Global Impression of Change (PGIC).
5. Perform dermal safety assessment (irritation, discomfort, and adhesion) and record the time of the evaluation for each assessment in the eCOA.
6. Review the subjects' eDiary entries. If there is any missing entry, re-instruct the subject to record the eDiary daily.
7. Collection of unused study drug and rescue medication (Note: At Visit 4, there will be no collection of rescue medication since the rescue medication is collected and not dispensed at Visit 3.).
8. Review subject's use of rescue medication/concomitant medication.
9. Perform drug accountability/reconciliation of study drug and rescue medication. The reconciliation (missing patch, failure of application, unscheduled detachment and application, etc.) will be recorded in the eCRF.
10. Dispense study drug and rescue medication and ensure subject has continued access to the eDiary.
11. Review AEs. The irritation and discomfort reported in the eDiary will be treated as AEs.

12. Re-instruct the subject concerning the patch application and removal method.
13. **Patient Education:** At all clinical study visits, the investigator (or designee) will explain the importance of the following:

- a. applying study drug [REDACTED] to the target knee after showering/bathing;
- b. keep the patch attached [REDACTED] including while sleeping;
- c. recording patient eDiary information [REDACTED] when subjects replace the patch, take any rescue medication and before they sleep;
- d. accurately reporting pain;
- e. accurately reporting rescue medication use;
- f. understanding when to return for their next visit and the importance of returning on schedule;
- g. adhering to the overall research plan; and
- h. Do NOT apply study drug to non-target knee at any time.

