##### **13.4.4.2 Dermal Performance**

The frequency and percentage of subjects and number of patches with findings related to dermal performance including irritation, discomfort, and adhesion will be summarized.

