###### **13.4.4.2.1 Irritation**

The frequency and percentage of subjects with patches in each combined and concatenated category will be summarized from the above scales at each visit and overall. The Concatenated Irritation score consists of numerical “Dermal Response” score + the “Other Effects” lettered score; for example: 2N, 2A, 3G, etc. The Combined irritation score will be calculated as a numerical total; i.e., numerical “Dermal Response” score + numeric equivalent for the “Other Effects” lettered score (note that the “Other Notations” do not have numeric equivalents and do not contribute to the numeric Combined irritation score); e.g., 2N, 2A, and 3G will be reported as 2, 2, and 6 combined irritations scores respectively.

Numeric equivalent for the “Other Effects” lettered score is A (0), B (1), C (2), F (3), G (3), H (3), N (0).

In addition to the above, the frequency and percentage of subjects with a combined score of 3 or more will be tabulated.

The information from eDiary data will be included in the summary table and listings.

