#### **13.4.4.2.4 Dermal Evaluations at Home**

At home, subjects will complete a questionnaire about skin irritation, discomfort, and adhesion in the eDiary. A by-subject listing of this data will be presented in addition to summary tables for each dermal assessment.

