#### **13.4.4.8 Dermal Safety**

The number and percentage of subjects with findings related to dermal safety including adhesion, irritation, and discomfort will be summarized. A by-subject listing of individual dermal safety findings will also be provided.

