3.3 CHANGES TO ANALYSIS FROM PROTOCOL

Not Applicable

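### SAP 18.7.2 summarises at-home dermal findings only as event counts, which depend on how many patches were worn and fall short of Protocol 13.4.4.2

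*SAP*

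**What the plan says.** SAP 18.7.2 covers the eDiary questionnaire on adhesion, irritation, discomfort and adhesive residue. It plans a by-subject listing and "summary tables for the number of events for each of the dermal assessments such as adhesion, irritation, discomfort", with residue included. Residue at Visit 8 is also summarised from a separate form. The section states no percentage, subject count or patch denominator. The clinic sections beside it do: adhesion by percentage of patches and by subjects' worst score (18.7.1.1), discomfort by number and percentage of subjects (18.7.1.2), and irritation by frequency and percentage of subjects (18.7.1.3).

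Protocol 13.4.4.2 sets the general rule: "The frequency and percentage of subjects and number of patches with findings related to dermal performance including irritation, discomfort, and adhesion will be summarized". Its irritation subsection adds: "The information from eDiary data will be included in the summary table and listings". The discomfort and adhesion subsections say much the same. Protocol 13.4.4.8 repeats the subject-level requirement: "The number and percentage of subjects with findings related to dermal safety including adhesion, irritation, and discomfort will be summarized". The subsection on home evaluations, 13.4.4.2.4, is looser: "A by-subject listing of this data will be presented in addition to summary tables for each dermal assessment".

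Under changes from the protocol, SAP 3.3 says "Not Applicable".

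**The concern.** Subjects answer the dermal questions each time they replace a patch (Protocol 10.1.3, procedures at home). The number of events a subject can contribute is therefore limited by the number of patches worn. In the later protocol text, subjects who stop treatment are encouraged to stay in the study without patches (8.2.3), so they add no further patch findings. The eDiary list for the Early Termination Visit (10.1.5) also omits the dermal questionnaire that the Visit 8 list contains.

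Wear time is not independent of the outcome, because poor skin tolerability is itself a reason to stop. If the arms differ in wear time, a comparison of raw counts is biased towards the arm with less exposure. Irritation, discomfort and adhesion are a stated objective and a safety endpoint, and the diary holds most of the patch-level information on them.

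**Working it through.** The plan gives no figure for at-home dermal data, and the sample size and replacement interval are redacted, so there is nothing of the plan's own to reproduce. The check has two parts.

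**1. Text.**
- Subjects with percentages: asked for in Protocol 13.4.4.2 and 13.4.4.8, with diary data fed into the summaries; absent from SAP 18.7.2.
- Number of patches with findings: asked for in Protocol 13.4.4.2. SAP 18.7.2 has events instead and does not define an event.
- Patches applied as a denominator: not required by Protocol 13.4.4.2 itself. SAP 14 already summarises patches applied by visit.

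**2. Arithmetic of the count.** From the documents: 1:1 allocation and 12 weeks (84 days). Assumed: 100 subjects per arm, about one patch per day, one event per patch record with a finding, and no stopping in arm A.

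*Raised rate throughout.* Ratio of counts (B/A) = rate ratio R × ratio of mean exposure. The order reverses when the exposure ratio is below 1/R:

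| R | Exposure ratio below | Mean days, of 84 |
|---|---|---|
| 1.25 | 0.80 | 67.2 |
| 1.5 | 0.667 | 56.0 |
| 2 | 0.50 | 42.0 |
| 3 | 0.333 | 28.0 |

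Short of reversal the contrast still shrinks: R = 1.5 with exposure at 80% shows as 1.5 × 0.80 = 1.20.

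*Reactive subset that stops early.* A share s of arm B has findings on a proportion rS of patches and stops at day d. Everyone else has arm A's rate rA.
- Events in A = 100 × 84 × rA
- Events in B = 100 × (1 − s) × 84 × rA + 100 × s × d × rS
- B falls below A when d × rS < 84 × rA

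With rA = 5%, s = 20%, rS = 50%, d = 7:
- A: 100 × 84 × 0.05 = 420 events on 8,400 patches, or 5.00 per 100.
- B: 80 × 84 × 0.05 + 20 × 7 × 0.50 = 336 + 70 = 406 events on 80 × 84 + 20 × 7 = 6,860 patches, or 5.92 per 100.
- The raw count puts B below A. The per-patch rate puts B above A.
- Subjects with at least one event: A 1 − 0.95^84 = 98.7%; B 0.8 × (1 − 0.95^84) + 0.2 × (1 − 0.5^7) = 98.8%. This measure hardly separates the arms here.

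With d = 14, B has 336 + 140 = 476 events. The order is right, but the count ratio is 476/420 = 1.13, against a per-patch ratio of 6.80/5.00 = 1.36.

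*How restrictive is reversal?* With rS = 50%, the stopping day must be below 84 × rA / 0.5: 8.4 days at rA = 5%, 3.36 at 2%, 1.68 at 1%. No scenario tried at rA = 1% reversed (stopping at days 3 to 28, s of 5% to 20%, rS of 50% or 100%). The largest reversal found was 420 against 366 (rA = 5%, s = 20%, rS = 50%, d = 3); most were small.

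**The case against.** The strongest reply is that irritation and discomfort do not rest on this table. The protocol says, in its Week 1 and 2 visit procedures and at later visits: "The irritation and discomfort reported in the eDiary will be treated as AEs". They therefore reach the adverse event tables, where SAP 18.1.1 provides that "The number and percentage of subjects with at least one TEAE and the number of TEAEs the subjects had will be presented". There is also an application-site table (18.1.5), a table of events leading to discontinuation with percentages (18.1.2), and a severity breakdown (18.1.1.1). A subject who stops on day 3 with severe irritation appears there as one affected subject and one discontinuation, however few diary records exist. SAP 14 summarises early patch removals and reasons. Clinic scoring is not confined to scheduled visits: the Early Termination Visit includes it, and subjects with significant or intolerable reactions are asked to arrange an unscheduled visit. All of this stands. It rules out the stronger inference a reader might draw, that the more irritating arm could come out as the milder one in the trial's overall report.

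Three further replies carry less weight. Protocol 13.4.4.2.4 names no measure for home data; but it sits under 13.4.4.2, which does, and the sibling subsections bring diary data in. SAP 8 bases percentages on subjects in the analysis set unless otherwise stated; but that fixes the denominator of a percentage and does not turn an event count into a subject count. The table shells mentioned in SAP 8 are not among the documents and may already carry subject columns; if so, the SAP text need only be brought into line.

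**Conclusion.** The point holds within the at-home tables. SAP 18.7.2 names one measure, it depends on exposure, and it is narrower than Protocol 13.4.4.2 with no change declared. Any difference in wear time between arms distorts the comparison. Reversal is possible but conditional, and in the scenarios tried it was mostly small.

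The trial-wide conclusion on irritation and discomfort is largely protected by the adverse event tables. What remains exposed is at-home adhesion and residue, which have no such route, and the per-patch rate of irritation and discomfort, which no planned table gives.

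The numerical part rests on assumed arm size, event rates, stopping pattern and daily replacement, and on counting each patch record with a finding as an event. The near-equal subject percentages arise because the illustration gives every non-reactive subject the same independent chance per patch; findings clustered in few subjects would saturate less. These tables are descriptive and no hypothesis test is affected. The change is still worth making because it costs little.

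**What to change.** In SAP 18.7.2, report by treatment arm, by visit and overall, for each at-home finding (adhesion including detachment, irritation, discomfort, residue):

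1. the number and percentage of safety-set subjects with at least one such finding;
2. the number of patches with the finding divided by the number of patches applied.

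Keep event counts as a supplement and define an event. Both measures are needed: subject percentages can saturate over 84 days, while a pooled per-patch rate gives little weight to subjects who wore few patches. If counts alone are really intended, SAP 3.3 should declare the departure from Protocol 13.4.4.2.

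The cost is SAP wording and table-shell columns. Patch application times and dermal answers are already in the eDiary, and patches applied by visit are already planned under SAP 14. No new data and no change to study conduct are needed.
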